Visit Description	Pre-screening (Phone/in person)	Baseline (Phone/in person)	Monitoring (Phone/in person)	Monitoring (Phone/in person)	Monitoring (Phone/in person)	Monitoring/Outcomes (Phone/in person)
Time point	Eligibility	Day 0	Day 7±3 days	Day 14±3 days	Day 28±3 days	Day 35±3 days
7 day pre-screening questionnaire	X					
Informed Consent	X					
Medical History /Physical Examination		X	X	X	X	X
Urine Pregnancy Test (Females of childbearing age)		X				
Washout	X					
Questionnaires		X		X		X
3-day food diary		X				
24-hour diet recall			X	X	X	X
Colonoscopy with mucosal biopsies (optional)	X					
Serum cytokine profiles (optional)		X				X
Buccal swab collection (optional)		X				
Glucose hydrogen breath testing		X				X
Stool collection for fecal microbial analysis		X (3 baseline samples)		X	X	X
Randomization	X					
Medication Dispensing		X				
Medication Compliance			X	X		
Adverse Events Monitoring			X	X	X	X

7 Data Collection and Management Procedures

Data Handling and Entry: All data including questionnaire results and physiologic testing will be recorded and reviewed by the study team. Data will then be entered into an electronic case report form (eCRF) that complies with Title 21 of the Code of Federal Regulations (21 CFR Part 11). All passwords will be strictly confidential to protect subject's protected health information (PHI). Only the Primary Investigator (PI) and Study Coordinator will have access to the data and subject identifiers. Only the PI and Study Coordinator will be allowed to enter data onto the password-protected web-based server.

Computer Systems: Data entry will be entered into REDCAP which is validated and conforms to regulatory requirements. Only the Primary Investigator (PI) and Study Coordinator will have access to the data and subject identifiers. Only the PI and Study Coordinator will be allowed to enter data onto the password-protected web-based server.

Phone Visits: All phone visits will be conducted with a University Health System phone to protect patient confidentiality.

SignNow: a secure application that enables users to electronically prepare and send University business documents for the purpose of requesting and obtaining digital signatures to help protect confidentiality.

Data Validation: Validation checks will be programmed within the eCRF system as well as supplemental validation performed by review of the downloaded data, will be applied to the data in order to ensure accurate, consistent, and reliable data.

Direct Access to Source Data: A developed review procedure that complies with Good Clinical Practice (GCP) guidelines.

Source Document/Case Report Form Completion: Source documents and the eCRFs will be completed for each study patient. It is the Investigator's responsibility to ensure the accuracy, completeness, and timeliness of the data reported in the patient's source document/eCRF. The source document/eCRF should indicate the patient's participation in the study and should document the dates and details of the study procedures, AEs, and patient status.

Record Retention: The Investigator will maintain all study records according to applicable regulatory requirement(s).

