2 OBJECTIVES

Aim 1: Randomize IBS-D subjects to receive either treatment with a nonabsorbable antibiotic rifaximin vs. low FODMAP dietary intervention.

- a) 200 IBS-D patients will be carefully phenotyped using validated questionnaires (IBS symptoms, stool form, psychological function, quality of life) and diet analysis.
- b) IBS-D subjects will undergo baseline testing including glucose hydrogen breath tests (GHBT) to define the presence of SIBO. Fecal microbiota will also be characterized by α - and β -diversity and dominant phyla on 16S RNA analyses.
- c) IBS-D subjects will be randomized to receive either rifaximin 550 mg three times daily $\times 14$ days or low FODMAP diet $\times 4$ weeks under direction of study bionutritionist.
- d) The primary outcome will be changes in mean daily pain or bloating by visual analog scale (VAS) after intervention compared with baseline. Responders to intervention will be defined by $\geq 30\%$ reductions in mean daily pain or bloating by VAS compared with baseline. Secondary outcomes will be defined by reduction in IBS Symptom Severity Scale by ≥ 50 compared with baseline.
- e) Other secondary outcomes, including GI symptoms, stool form, psychological function, quality of life, and diet intake, will be compared to determine if subjects present differently.

Aim 2: Determine using longitudinal analyses how SIBO status and fecal microbiota features associate with response to treatment with rifaximin or a low FODMAP dietary intervention.

- a) Fecal microbial analyses will be repeated at 2, 4 and 5 weeks while GHBT will be repeated at the end of the intervention.

- b) The primary aim will be change in fecal microbial diversity after intervention compared with baseline. We hypothesize that low FODMAP diet will result in a 10-15% increase in diversity in fecal microbiota compared with baseline.
- c) Secondary outcomes including response to treatment with rifaximin or low FODMAP diet will be related to the (i) presence of SIBO on initial testing, (ii) persistence of SIBO after intervention, (iii) abnormal α - and β -diversity on initial testing, (iv) changes in α - and β -diversity as well as in dominant microbial phyla at 2, 4 and 5 weeks, and (v) changes in serum cytokine profiles, including TNF- α , IL-1 β , IL-6, IL-8, and IL-10.

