6 STUDY DESIGN AND PROCEDURES

Specific Aim 1: Randomize IBS-D subjects to receive either a nonabsorbable antibiotic rifaximin vs. low FODMAP dietary intervention.

1A. Research Approach:

200 IBS-D subjects will be carefully phenotyped using validated questionnaires (IBS symptoms, stool form, psychological function, quality of life) and diet analysis. IBS-D subjects will also undergo baseline testing including GHBT as well as fecal microbial analysis. IBS-D subjects will then be randomized to receive either rifaximin or low FODMAP diet intervention at the initial screening visit. Efficacy of therapies will be monitored with validated questionnaires to track symptomatic improvement. The primary outcome will be changes in mean daily pain or bloating after intervention compared with baseline. Responders to intervention will be defined as $\geq 30\%$ reduction in mean daily pain or bloating by visual analog scale (VAS) compared with baseline. Secondary outcomes will monitor changes in IBS-Symptom Severity Score as well as differences in GI symptoms, stool form, psychological function, quality of life, and dietary intake before and after intervention.

1B. Experimental Methods:

Subject Recruitment: 200 adult subjects ≥ 18 years of age who meet Rome IV criteria for IBS-D will be enrolled in the study. Women of childbearing age will undergo a urine pregnancy test to exclude the possibility of pregnancy. Women who are breastfeeding will also be excluded. IBS-D subjects will be excluded if they have underlying celiac disease, inflammatory bowel disease, or other organic disease that could explain their symptoms. All IBS-D subjects will have prior sigmoidoscopy or colonoscopy with mucosal biopsies within the past 2 years to rule out microscopic colitis. IBS-D subjects with a history of GI tract surgery, except for appendectomy, will also be excluded from the study. Antibiotics taken within 3 months prior to enrollment will not be permitted (54). IBS-D subjects on probiotics must discontinue their use at least 1 month prior to fecal collection. IBS medications, including anti-depressants, will be allowed if the dose has been stable for at least 1 month before inclusion. Medications will be carefully tracked to follow any potential confounding issues. IBS-D subjects who have previously received formal

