dietary education for IBS, including a low FODMAP diet, or previously received antibiotics, including rifaximin, for treatment of IBS-D or SIBO will be excluded from the study.

GI Symptom Assessment: All IBS-D subjects will complete validated questionnaires to quantify severity of IBS symptoms, including IBS Symptom Severity Scale (IBS-SSS), Gastrointestinal Symptom Rating Scale-IBS (GSRS-IBS), an 11-point numerical rating scale (NRS) for abdominal pain and bloating, and Bristol Stool Form Scale (BSFS) at baseline (55–58). The NRS for abdominal pain and bloating and the BSFS will be completed online through the REDCap Survey Tool.

Psychological and Quality of Life Assessment: IBS-D subjects will also complete validated questionnaires to assess for presence of and to measure severity of psychological disorders, GI specific anxiety, and impairments in quality of life. All IBS-D subjects will complete the Patient Health Questionnaire (PHQ-9), Visceral Sensitivity Index (VSI), and IBS-quality of life (IBS-QOL) (59–61). The PHQ-9 will be reviewed by the study team within 24 hours of completing the questionnaire. If a subject answers affirmative to the question “Thoughts that you would be better off dead or of hurting yourself in some way,” they will be provided with the appropriate referral to mental health counseling and/or the subject’s PCP will be alerted.

Dietary Assessment: All IBS-D subjects will undergo initial consultation with the study team and will be instructed on how to monitor and record their dietary intake. IBS-D subjects will then record daily their dietary intake for 3 days prior to fecal collection.

Fecal Collection and Preparation: Three fresh stool samples will be collected from all IBS-D subjects at baseline. Each sample will be immediately placed into an OMNIgene•GUT collection tube (DNA Genotek, Inc., Ottawa, ON, Canada) which allows for self-collection and stabilization of fecal DNA samples for up to 60 days at ambient temperature (62). Samples will then be mailed back or picked up by the study team and stored at -80°C in [name]’s Lab for long-term storage. If patients consent to the optional portion of the study, they will provide a stool sample in 95% ethanol at Visits 1, 3, 4, and 5. We will also collect a one-time stool sample and symptom questionnaires from healthy controls. Healthy controls will not have a history of gastrointestinal conditions and do not report any abnormal bowel movements or abdominal pain.

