We will develop and validate a predictive model of response to low FODMAP diet using data from the subjects randomized to a low FODMAP diet (Aim 1) combined with existing data from a separate cohort of IBS-D subjects previously treated with a low FODMAP diet (HUM 00053274).

3B. Experimental Methods:

We will use the combined cohort of patients treated with a low FODMAP diet (Aim 1 and HUM #00053274), which will be split into a training set from a random sample of 80% of the data while the remaining 20% of the data will serve as the test set. Using a random forest model, 5x2 nested cross-validation (CV) will be performed within the training set for model selection and hyperparameter tuning. The candidate models will be compared by testing for overlap of confidence intervals for area under the curves (AUCs, two-sided test). Once a final model is selected, model performance will be evaluated on the test set.

Study Timeline:

Figure 1 IBS Subject Timeline

Schedule of Events - Low FODMAP Group

Visit Number	Pre-Visit	Visit 1	Visit 2	Visit 3	Visit 4	Visit 5
Visit Description	Pre-screening (Phone/in person)	Baseline (Phone/in person)	Monitoring (Phone/in person)	Monitoring (Phone/in person)	Monitoring (Phone/in person)	Monitoring/Outcomes (Phone/in person)
Time point	Eligibility	Day 0	Day 7±3 days	Day 14±3 days	Day 28±3 days	Day 35±3 days
7 day pre-screening questionnaire	X					
Informed Consent	X					
Medical History /Physical Examination		X	X	X	X	X
Urine pregnancy test (Females of childbearing age)		X				
Washout	X					
Questionnaires		X		X		X

3-day food diary		X				
24-hour dietary recall			X	X	X	X
GI nutrition consultation		X		X		
Colonoscopy with mucosal biopsies (optional)	X					
Serum Cytokine Profiles (optional)		X				X
Buccal swab collection (optional)		X				
Glucose hydrogen breath testing		X				X
Stool collection for fecal microbial analysis		X (3 baseline samples)		X	X	X
Randomization	X					
Dietary Compliance			X	X	X	X
Adverse Events Monitoring			X	X	X	X

*Female participants capable of bearing children will be required to attend visit 1 in person for the pregnancy test

*During COVID-19 pandemic, all hydrogen breath tests will be conducted remotely

Schedule of Events – Rifaximin Group

*Female participants capable of bearing children will be required to attend visit 1 in person for the pregnancy test

*During COVID-19 pandemic, all hydrogen breath tests will be conducted remotely

Visit Number	Pre-Visit	Visit 1	Visit 2	Visit 3	Visit 4	Visit 5

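### Section 6 text puts randomisation after baseline testing, but both schedules mark it at Pre-Visit, before the Visit 1 pregnancy test and baseline measures

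*Combined protocol and SAP*

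**What the plan says.** **Text.** Section 6, 1A Research Approach, describes phenotyping, diet analysis, the breath test and fecal sampling, and continues: "IBS-D subjects will then be randomized to receive either rifaximin or low FODMAP diet intervention at the initial screening visit". Section 2, Aim 1, lists the steps in the same order. Item (b) is "IBS-D subjects will undergo baseline testing including glucose hydrogen breath tests (GHBT) to define the presence of SIBO", and randomisation follows as item (c).

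**Schedules.** In both Schedules of Events (low FODMAP and rifaximin) the row reads "Randomization X", with its only mark in the Pre-Visit column, whose time point is Eligibility. The pregnancy test, questionnaires, 3-day food diary, breath test and stool collection are first marked at Visit 1 (Day 0). The stool entry there is "X (3 baseline samples". A footnote to both schedules confirms the place of the pregnancy test: "Female participants capable of bearing children will be required to attend visit 1 in person for the pregnancy test". On the diary, Section 6 (Dietary Assessment) says: "IBS-D subjects will then record daily their dietary intake for 3 days prior to fecal collection".

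**Start of treatment.** The first nutrition consultation (diet arm) and the row "Medication Dispensing" (rifaximin arm) are also first marked at Visit 1.

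**Rules that depend on the order.** Section 4 excludes pregnant women. Section 5 says that subjects who fail the criteria are not enrolled. Section 10 specifies intention-to-treat and uses each subject as his or her own control. For Aim 2, Section 2 states: "The primary aim will be change in fecal microbial diversity after intervention compared with baseline".

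**The concern.** The point of randomisation fixes who belongs to the intention-to-treat population and which measurements count as unaffected by allocation. The plan gives two different points.

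Two things are at stake if staff follow the schedules. First, an exclusion criterion is tested after the subject has been allocated. Second, the baselines for Aim 2's primary outcome, for IBS-SSS and for diet are collected after allocation. The comparison is a pill against a diet, and no masking is described. A subject who has learned the arm could change what he or she eats or reports before the baseline is complete. Section 1 itself notes that diet strongly affects the gut microbiota.

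**Working it through.** No power or sample-size arithmetic applies. The check sets the passages side by side.

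**1. Order in each source**

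| Step | Section 6, 1A (same order in Section 2, Aim 1 b–c) | Both schedules |
|---|---|---|
| Questionnaires, diet record | before randomisation | Visit 1 |
| Breath test, fecal sampling | before randomisation | Visit 1 |
| Urine pregnancy test | not placed in 1A; 1B gives its purpose as exclusion | Visit 1 |
| Randomisation | after the baseline tests; at an initial screening visit | Pre-Visit |
| Nutrition consultation or dispensing | not timed in 1A | Visit 1 |

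**2. Can the sources be reconciled?** Neither schedule has a column called the initial screening visit.
- If it means Pre-Visit, the 1A sentence agrees with the schedules on the visit. Its word *then* fails, because the baseline tests come later, at Visit 1.
- If it means Visit 1, *then* holds, but the mark in both schedules is wrong.

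Neither reading satisfies all the passages.

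**3. Is it an artefact of table extraction?** Unlikely. Neighbouring rows keep their columns: consent and washout fall at Pre-Visit, the pregnancy test and breath test at Visit 1. The Randomization mark sits in the same place in two separate tables.

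**4. Consequence for eligibility.** Under the schedules the sequence is randomise, then test for pregnancy, then exclude if positive. Section 10 does not say how an exclusion after randomisation is handled. The sequence also sits badly with Section 5, under which ineligible subjects are not enrolled.

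**5. Consequence for the change scores.** Each subject's change is d = Y − B, with Y the later value and B the baseline. If B moves by s because the subject already knows the arm, d moves by −s. For α-diversity, Section 10 averages three baseline samples: B = (B1 + B2 + B3)/3. If k of the three move by s, then B moves by k·s/3 and d by −k·s/3. All three are first marked at Visit 1, so k can be anything from 0 to 3. If only one arm shifts, the difference between arms moves by the same amount. The documents give nothing from which to set s or k, so no numerical bias follows.

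The 3-day diary has the same exposure. It runs up to the stool collection, so its days can also fall after allocation.

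**6. What is not touched.**
- Section 5 puts the 7-day pain and bloating pre-screen before consent, so it precedes allocation under either order.
- Section 10, Aim 2, says that the three stools are taken before treatment. That is compatible with both orders and does not settle their place relative to randomisation.

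**The case against.** The strongest reply is that the conflict hangs on one word. Both schedules label Pre-Visit as pre-screening, which is a natural match for an initial screening visit. The items under Aim 1 may be a list of design elements rather than a timetable. A Randomization mark does not say when the subject learns the arm: the allocation could be generated at Pre-Visit and disclosed later. Section 11.3.1 makes the investigator responsible for eligibility, and positive pregnancy tests may be rare. The breath test is an objective measure, and Section 3 asks every subject to follow the same low-carbohydrate preparation before it.

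Much of this stands. The 1A sentence is ambiguous in itself, disclosure at Pre-Visit is possible but not stated, and the breath test is the baseline least exposed. None of it removes the contradiction. If the initial screening visit is Pre-Visit, the sentence contradicts itself once it is read with the schedules. A general duty to check eligibility does not say that the Visit 1 test comes before allocation.

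A reader might infer more: that subjects will know their arm, or will have started treatment, before baseline, or that the pain and bloating result is biased. The documents do not support this. They do not say when the arm is disclosed, they schedule neither treatment before Visit 1, and the pre-screen week may be the symptom baseline.

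**Conclusion.** Wrong as written. The 1A sentence and the two schedules cannot all be followed, and this needs no assumed input.

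The consequences are conditional. If the schedules are followed, a positive pregnancy test is a post-randomisation exclusion. The diversity, IBS-SSS and diet baselines are then post-allocation. Bias in the changes arises only if subjects also learn their arm before those measures are complete and act on it. Its size cannot be estimated: the documents give no interval from Pre-Visit to Visit 1, no rate of early diet change and no rate of positive tests.

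For pain and bloating, the conclusion depends on which week is the baseline. Those outcomes are unaffected if it is the pre-screen week. Section 6 (GI Symptom Assessment) also lists the same scale among the baseline questionnaires, so this cannot be taken as settled.

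**What to change.** In both schedules, move the Randomization mark from Pre-Visit to Visit 1 and define it as the last step before treatment begins. It should come:
- after eligibility is confirmed, including the pregnancy test;
- after the baseline questionnaires, 3-day diary, breath test and three stools are collected;
- before the nutrition consultation or medication dispensing.

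In Section 6, 1A, replace the reference to the initial screening visit with the end of Visit 1 (Day 0). This restores the order that 1A and Section 2 already describe.

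Allocation need not wait for breath-test or sequencing results, because Section 4 does not make them eligibility criteria. The breath test, diary and stools are already all marked at Visit 1, so moving the mark does not create any overlap between the breath-test preparation and the other two.

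**Cost.** No new measure or assay is needed. Some baseline kits will be used by subjects who are then not randomised, and a nutrition slot must be held before the arm is known.

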5 SUBJECT ENROLLMENT

Most patients with irritable bowel syndrome are seen in gastroenterology or general medicine clinics. IBS-D patients will be recruited from gastroenterology and general medicine clinics at Taubman Center and in the satellite clinics within the University of Michigan Health System. We will also be sending out letters to patients identified from DataDirect as eligible for the study. Eligible IBS-D subjects will be contacted and given material explaining the nature of the study and introduction to a low FODMAP diet. They will be given time to read the materials. If they choose to participate, they will undergo a one week pre-screening an 11-point numerical rating scale (NRS) for abdominal pain and bloating for 7 days. If the subjects qualify through the pre-screen, they will sign the consent document in the presence of the PI and/or Designee. IBS-D subjects will be enrolled on a first come, first served basis. This approach will ensure that IBS-D subjects are representative of the population of patients with IBS in Southeast Michigan.

Emails to providers in the General Medicine and Gastroenterology clinics in the University of Michigan System, public advertisements, telephone calls, and web postings on UMClinicalStudies.org will also be utilized to recruit IBS-D subjects.

IBS subjects who do not meet inclusion/exclusion criteria will not be enrolled in the study. All data collected from IBS-D subjects who are screen failures will be saved for data analysis.

IBS subjects and healthy controls who are undergoing colonoscopy will be approached in the Medical Procedures Unit to determine their interest in participating in the optional sub-study and to determine their eligibility.

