Trial Protocol: In order to minimize unequal allocation between arms, IBS-D subjects will be randomized using block randomization with random permuted sizes of 2 or 4 in a 1:1 ratio into two arms: one group will undergo treatment with rifaximin 550 mg three times daily for 14 days. The second group will be placed on a low FODMAP diet (≤ 9 grams per day as previously described) for 4 weeks (40,64,65). IBS-D subjects undergoing dietary intervention will undergo consultation with a bionutritionist knowledgeable in low FODMAP diets. A diet plan will be implemented and individualized to subjects based on information from their dietary history. Written information regarding allowable vs. non-allowable food items will be provided to IBS-D subjects and bionutritionists will be available during the study for further education. IBS-D subjects randomized to the low FODMAP diet group will meet with the GI nutritionist at the completion of the 2nd week of dietary intervention to answer any potential questions regarding the diet. IBS-D subjects will complete a 24-hour dietary recall each week or every two weeks during the 4-week dietary intervention to ensure compliance.

Symptom Assessment: IBS-D subjects will record stool frequency, BSFS, and symptom scores for abdominal pain and bloating daily on a diary card. IBS-D subjects will complete questionnaires on a weekly basis during study visits to determine changes in symptoms. Responders to intervention arm (both rifaximin and low FODMAP diet) will be defined as $\geq 30\%$ reductions in mean daily pain or bloating compared with baseline. Secondary outcomes, including reduction in IBS Symptom Severity Scale by ≥ 50 compared with baseline at the end of the interventional arm, will also be monitored. These are both considered to reflect clinically meaningful improvements in IBS (55,57). IBS-D subjects will be seen on a weekly or biweekly basis and diary cards will be collected. Adherence to medications or dietary intervention will also be assessed at that time.

Specific Aim 2: Determine using longitudinal analyses how SIBO status and fecal microbiota-derived metrics associate with response to treatment with rifaximin or a low FODMAP dietary intervention.

2A. Research Approach:

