10 STATISTICAL CONSIDERATIONS

Aim 1:

All of the interventional analyses will be analyzed on an intention-to-treat basis. Each IBS-D subject will act as his/her own control for analysis of the effects of either rifaximin or low FODMAP diet intervention. This paired design inherently eliminates a significant amount of bias/confounding and affords increased statistical power. We will power our study to detect a $\geq 30\%$ improvement in mean daily bloating or abdominal pain after intervention compared with baseline. Using available data from a US study on low FODMAP diet in IBS patients (42), we conservatively estimate that we will require 14 IBS-D subjects in each arm to have $>90\%$ power to detect a mean difference of 1.7 in abdominal bloating scores after intervention via paired t-tests with the expected standard deviation (SD) of ± 1.8 . Thus, our expected enrollment of 32 IBS-D subjects in each arm will be more than sufficient for analyzing this aim (see biostatistical analysis for Aim 2), even if the SD is nearly two-fold larger than expected.

Aim 2:

We will examine both inter- and intra-individual variability in microbiota-derived metrics. We plan to use a paired design to eliminate a significant amount of bias/confounding and increase statistical power. We anticipate that there will be some variability in the three samples collected prior to treatment, and various techniques will be employed to average these data so they are incorporated as the baseline. For example, for α diversity (Shannon index) a simple average of the three time points will be sufficient to

establish a baseline α diversity. Similar techniques will be applied to other community structure metrics, to create “deltas” between post-treatment time points and the baseline.

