11 REGULATORY REQUIREMENTS

11.1 Informed Consent ¹

¹ The IRB may waive some or all elements of informed consent – consult the IRB for consenting requirements.

Informed consent will be signed by subjects after the protocol is explained by either the PI, co-I or study coordinator. If an IBS-D subject is a patient of the PI or Co-I, the study coordinator will be responsible for obtaining informed consent to avoid potential issues of coercion. Before signing, IBS-D subjects will be given ample opportunity to ask questions about the protocol. Consent forms could be signed in the Taubman Center or in the GI Physiology Laboratory in the Medical Procedures Unit. Please see Informed Consent attached as an appendix.

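### Blocks of 2 or 4 are printed in the protocol of a visibly unmasked trial with no concealment step described: a team tracking the sequence would guess 72% of assignments, and a less predictable scheme costs almost nothing

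*Combined protocol and SAP*

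**What the plan says.** Section 6 (1B, Trial Protocol) allocates by "block randomization with random permuted sizes of 2 or 4 in a 1:1 ratio". The reason given is balance of numbers: "In order to minimize unequal allocation between arms". No stratification factor is named. The text does not say who generates or holds the list, how an assignment is released, or what must be recorded first.

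The arms cannot look alike: "one group will undergo treatment with rifaximin 550 mg three times daily for 14 days", and "The second group will be placed on a low FODMAP diet", with a bionutritionist. No placebo or sham is described. Masking is not mentioned, so open-label status is an inference from the treatments.

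Recruitment takes place at the main centre and "in the satellite clinics within the University of Michigan Health System" (section 5). On consent, section 11.1 states: "Informed consent will be signed by subjects after the protocol is explained by either the PI, co-I or study coordinator". Section 7 gives the principal investigator and coordinator access to data and identifiers. Section 6 places randomization at the initial screening visit, and both schedules of events mark consent and randomization in the same Pre-Visit column, with no stated order.

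The documents conflict on size. Section 6 has "200 IBS-D subjects will be carefully phenotyped using validated questionnaires", while section 10 has "our expected enrollment of 32 IBS-D subjects in each arm will be more than sufficient", which is 64 in all.

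**The concern.** Small permuted blocks force the arms back to equality every two or four patients. Anyone who knows the possible sizes and sees past assignments can often tell which arm is due. Here the sizes are in the document the team works from, and the same few people enrol patients and see what each one received.

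Foreknowledge matters only if it can influence who is enrolled, or when. Most entry criteria are objective, but the exclusion for other organic disease needs judgement, and the timing of enrolment is in the team's hands. If enrolment depended on the expected arm, the arms could differ at baseline for reasons other than chance. That would distort any comparison of rifaximin with diet under Aim 1. It would also change the patients behind the response associations of Aim 2 and the low-FODMAP prediction model of Aim 3.

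**Working it through.** **Plan's own figure.** The plan gives no figure for predictability. Its sample-size figure for Aim 1 (14 per arm, paired t-test, difference 1.7, SD 1.8, more than 90% power) reproduces: 87.8% at n = 13 and 90.4% at n = 14, assuming two-sided 5%. It matters here only because it shows that the powered test is within-arm.

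**Inputs.** Block sizes 2 and 4 and the 1:1 ratio are from section 6. The chance of each size is not stated; 50/50 is assumed, with all-2 and all-4 as the range. The observer knows the possible sizes and all past assignments, but not the current block's size.

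**Step 1: correct guesses.** Guessing the arm that is behind gives m + 2^(2m−1)/C(2m, m) − 1/2 expected correct guesses in a block of 2m.
- Block of 2: 1 + 2/2 − 0.5 = 1.5.
- Block of 4: 2 + 8/6 − 0.5 = 2.833.
- Mixture: (1.5 + 2.833)/(2 + 4) = 72.2%. The range is 70.8% (all 4) to 75% (all 2).

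That is about 144 of 200 patients, or 46 of 64. Simulation of an optimal Bayesian guesser gives the same 72% at both sizes.

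**Step 2: how it is distributed.**
- Arms unequal before the assignment: once in a block of 2. In a block of 4, always before positions 2 and 4, and with probability 1/3 before position 3. Share: (1 + 2.333)/6 = 55.6%. The other 44.4% are coin tosses.
- Accuracy when unequal: expected correct guesses are 1 in a block of 2 and 2/3 + 1/3 + 1 = 2 in a block of 4, so 3/3.333 = 90% on average. Check: 0.444 × 0.5 + 0.556 × 0.9 = 72.2%.
- The weakest informed guess, just after a block is known to have started, is right with probability 1/2 × 1 + 1/2 × 2/3 = 83.3%. All informed guesses therefore pass 75%.
- Certain with the block size hidden: a block of 4 that opens with the same arm twice (probability 1/3) fixes its last two places. Share: 2 × (1/3)/6 = 11.1%. If the current block size were known, the share would be 38.9%.
- By simulation, about 16% of assignments are at least 90% predictable, the certain ones included.

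**Step 3: alternatives at N = 200.** Relative efficiency is 4·n1·n2/N².

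| Scheme | Correct guesses | Better than coin toss | At least 75% | Certain | Worst split | Efficiency |
|---|---|---|---|---|---|---|
| Blocks 2/4 | 72% | 56% | 56% | 11% | 101:99 | 99.99% |
| Blocks 4/6/8 | 68% | 64% | 34% | 2% | 102:98 | 99.96% |
| Big stick, limit 6 | 54% | 8% | 8% | 8% | 103:97 | 99.91% |

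Under big stick every assignment is a coin toss except at the limit, where it is forced. A long-run share of 1/(11 + 1) = 8.3% falls at the limit, slightly less when the list starts from balance. Correct guesses are then 0.5 + 0.5 × 0.08 = 54%. The 8% assumes the observer knows the limit.

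At N = 64 the worst splits are 34:30 for blocks 4/6/8 (4 × 34 × 30/4096 = 99.6%) and 35:29 for big stick (4 × 35 × 29/4096 = 99.1%).

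**The case against.** There is a fair case for leaving this alone. Randomly varied block sizes are already a measure against prediction. Patients enter consecutively, first come, first served, after a scored seven-day pre-screen and with Rome IV criteria, which narrows the room to steer. Section 10 uses each patient as his or her own control and specifies no between-arm test for Aim 1. Larger blocks alone move correct guesses only from 72% to 68%, about 8 patients in 200. The choice of cut-off also matters: 4/6/8 looks clearly better at 75%, but it leaves more assignments above a coin toss (64% v 56%). Big stick has its own forced assignments.

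Most of this stands, and it limits the claim. It argues for not relying on larger blocks alone, and it keeps the point away from the powered analysis. It does not remove the concern. Aim 1 still randomizes rifaximin against diet, the entry criteria leave some discretion, and no concealment step is described.

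A reader might infer that the team can know most assignments in advance. The figures do not support that: 11% are certain, about 16% are at least 90% predictable, and nearly half are coin tosses. A reader might also infer that patients are being steered. Nothing in the documents shows this, and it would require the team to track the order of assignments.

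**Conclusion.** The point holds as a cheap improvement to the design. With the printed scheme, visible treatments and one team enrolling and holding the data, the best guess is right 72% of the time, and 55% of assignments can be called with at least 83% probability. This rests on three assumptions: equal chance of each block size (70.8% to 75% over the full range), a team that follows the sequence, and no concealment procedure beyond what the text describes. It does not depend on whether 200 or 64 patients are randomized.

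What is exposed is the between-arm comparison and the make-up of the arms used in Aims 2 and 3. The within-arm paired test is less directly affected. The tight balance bought by blocks of 2 is worth almost nothing in a single unstratified list.

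**What to change.** For all remaining assignments:

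1. Replace the blocks with a maximum-tolerated-imbalance rule such as big stick with limit 6. At the least, drop blocks of 2 in favour of larger mixed blocks such as 4, 6 and 8, accepting that the gain is modest.
2. Remove the block sizes or the limit from the protocol. Keep them with a list generator who does not enrol patients.
3. State that each assignment is released through REDCap, already used in the study, only after consent and eligibility are recorded and locked.

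The cost is a new list, a REDCap set-up step and a short protocol change. The downside is a slightly larger possible imbalance: a final difference of at most 6 under big stick or 4 under blocks of 4, 6 and 8. At 200 patients that loses less than 0.1% of efficiency; at 64, less than 1%.
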